11.3 Clinical laboratory evaluations

Clinical laboratory parameters (blood chemistry, hematology, urinalysis, and endocrinology) are assessed at all FEVs, YEVs, EDVs, and at FV and may also be assessed at Unscheduled Visits.

11.3.1 Hematology and blood chemistry parameters

Observed values for each planned hematology and blood chemistry parameter will be summarized for Baseline, Study Entry, and each scheduled visit during the Evaluation Period for which laboratory parameters were assessed, Last Value, EDV, and FV. Change from Baseline will be summarized for all post-Baseline time points including EV. Only laboratory parameters planned per protocol will be summarized; results for laboratory parameters not planned per the protocol will only be provided in subject data listings.

The number and percentage of subjects with an on-treatment potentially clinically significant treatment-emergent (PCST) value, PCST low value, and PCST high value will be summarized. This summary will consider all assessments after the first dose of BRV and prior to or on the date of the last dose of BRV. Percentages will be relative to the number of subjects with an on-treatment assessment.

Additionally, the number and percentage of subjects with a PCST value, PCST low value, and PCST high value will be summarized for Baseline, Study Entry, each visit during the Evaluation Period for which laboratory parameters were scheduled to be assessed, EDV, Last Value, and FV. Percentages for each parameter and time point will be relative to the number of subjects with a value at that time point.

PCST criteria (Sections 13.3 and 13.3.2) are based on FDA Division of Neuropharmacologic Drug Products guidelines with some UCB-defined additions.

Creatinine clearance, when available from the central laboratory, will be provided in subject data listings only and will not be summarized.

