5.4 Rationale for study design and selection of dose

In the previous study N01358, subjects will be randomized to an oral dose of BRV 100mg/day, BRV 200mg/day, or to matching PBO. In the previous study N01258, subjects will receive either a 60-second iv bolus or a 15-minute iv infusion at a dose of BRV 100mg twice daily (200mg/day). Previous Phase 2/3 clinical studies in POS and dose-response modeling suggest that optimal seizure frequency requires BRV doses of 50 to 100mg/day, with BRV 150mg/day possibly providing some additional benefit. Following consultation with regulatory authorities, it was recommended to also explore BRV 200mg/day to obtain data on the upper end of the dose response curve in N01358.

The starting doses in N01379 will be BRV 150mg/day for subjects from N01358 and BRV 200mg/day for subjects from N01258. The study entry doses will be taken as 2 equally divided oral doses administered twice daily. In Phase 2/3 studies for POS with BRV doses up to 150mg/day, the overall discontinuation rate and the discontinuation rate due to TEAEs was low and similar to PBO. The most frequently reported TEAEs at BRV doses up to 150mg/day were headache, somnolence, dizziness, and fatigue. The BRV dose can be adjusted based on the individual subject's seizure control and/or tolerability after the first 2 weeks, up to a maximum dose of BRV 200mg/day.

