3.2 Analysis time points

3.2.1 First and last dose of BRV

Unless otherwise noted, all references to the first dose of BRV in this SAP refer to the first dose of BRV during N01379 (ie, not the first dose of BRV from the previous study in which subjects participated in prior to N01379). Unless otherwise noted, all references to the last known dose of BRV in this SAP refer to the last dose of BRV taken across any study periods (ie, not necessarily the last dose of BRV during the Evaluation Period).

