3.3 Definition of Baseline Values

Baseline for all study outcomes will be based on baseline from the previous studies. For assessments performed at scheduled and unscheduled visits, Baseline will generally be the last result obtained or prior to the randomization visit of the previous study. Baseline will be defined separately for each hematology, blood chemistry, urinalysis, and endocrinology parameter.

Baseline for the evaluation of seizure frequency and seizure days will be calculated from the core study seizure diary based on the rules defined in Section 3.8.1.

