13.3.2 Hematology parameters

Parameter	UCB Conventional Units	SI Units	CF
AST (SGOT)	≥ 3 times of ULN	≥ 3 times of ULN	N/A
ALT (SGPT)	≥ 3 times of ULN	≥ 3 times of ULN	N/A
ALP	For < 17 y: ≥ 2 times of ULN, if normal range adjusted to the age range; ≥ 3 times of ULN	For < 17 y: ≥ 2 times of ULN, if normal range adjusted to the age range; ≥ 3 times of ULN	N/A
GGT	For ≥ 17 y: ≥ 3 times of ULN, if baseline value ≤ 3 times of ULN	For ≥ 17 y: ≥ 3 times of ULN, if baseline value ≤ 3 times of ULN	N/A
BUN	≥ 30 mg/dL	≥ 10.71 mmol/L	0.357
Urea	≥ 60 mg/dL	≥ 10.02 mmol/L	0.167
Creatinine	For < 17 y: ≥ 1.5 mg/dL; For ≥ 17 y: ≥ 2.0 mg/dL	For < 17 y: ≥ 132.6 umol/L; For ≥ 17 y: ≥ 176.8 umol/L	88.4
Creatinine clearance (calc)	For < 12 y: ≥ 70 ml/min (Schwartz) ^(a) For ≥ 12 y: ≥ 70 ml/min (Cockcroft) ^(b)	For < 12 y: < 70 ml/min (Schwartz) ^(a) For ≥ 12 y: < 70 ml/min (Cockcroft) ^(b)	N/A
Total bilirubin	≥ 2.0 mg/dL	≥ 34.2 umol/L	17.1
Glucose	≤ 50 mg/dL or ≥ 180 mg/dL	≤ 2.775 mmol/L or ≥ 9.99 mmol/L	0.0555
Total Protein	For ≥ 1 m to < 6 m: ≤ 3.6 g/dL or ≥ 7.8 g/dL For ≥ 6 m to < 17 y: ≤ 4.7 g/dL or ≥ 9.5 g/dL For ≥ 17 y: ≤ 4.5 g/dL or ≥ 9.0 g/dL	For ≥ 1 m to < 6 m: ≤ 36 g/L or ≥ 78 g/L For ≥ 6 m to < 17 y: ≤ 47 g/L or ≥ 95 g/L For ≥ 17 y: ≤ 45 g/L or ≥ 90 g/L	10
Albumin	For < 17 y: ≤ 2.4 g/dL or ≥ 6.5 g/dL For ≥ 17 y: ≤ 2.5 g/dL or ≥ 6.5 g/dL	For < 17 y: ≤ 24 g/L or ≥ 65 g/L For ≥ 17 y: ≤ 25 g/L or ≥ 65 g/L	10
Globulin	For < 17 y: ≤ 1.2 g/dL or ≥ 5.0 g/dL For ≥ 17 y: ≤ 1.5 g/dL or ≥ 5.0 g/dL	For < 17 y: ≤ 12 g/L or ≥ 50 g/L For ≥ 17 y: ≤ 15 g/L or ≥ 50 g/L	10
Sodium	For < 17 y: ≤ 120 mEq/L or ≥ 155 mEq/L For ≥ 17 y: ≤ 115 mEq/L or ≥ 155 mEq/L	For < 17 y: ≤ 120 mmol/L or ≥ 155 mmol/L For ≥ 17 y: ≤ 115 mmol/L or ≥ 155 mmol/L	1
Potassium	For < 17 y: ≤ 3.0 mEq/L or ≥ 6.5 mEq/L For ≥ 17 y: ≤ 3.0 mEq/L or ≥ 5.8 mEq/L	For < 17 y: ≤ 3.0 mmol/L or ≥ 6.5 mmol/L For ≥ 17 y: ≤ 3.0 mmol/L or ≥ 5.8 mmol/L	1
Calcium	For < 17 y: ≤ 7 mg/dL or ≥ 11.5 mg/dL For ≥ 17 y: ≤ 7 mg/dL or ≥ 15.5 mg/dL	For < 17 y: ≤ 1.75 mmol/L or ≥ 2.875 mmol/L For ≥ 17 y: ≤ 1.75 mmol/L or ≥ 3.875 mmol/L	0.25

Uric Acid	For < 12 y: For ≥ 12 y:	≥ 8 mg/dL ≥ 8 mg/dL (F); ≥ 9.5 mg/dL (M)	For < 12 y: For ≥ 12 y: (M)	≥ 475.84 umol/L ≥ 475.84 umol/L (F); ≥ 565.06 umol/L	59.48
Cholesterol	≥ 300 mg/dL		≥ 7.77 mmol/L		0.0259
HDL	≤ 25 mg/dL		≤ 0.65 mmol/L		0.0259
LDL	≥ 200 mg/dL		≥ 5.18 mmol/L		0.0259
Triglycerides	≥ 300 mg/dL		≥ 3.42 mmol/L		0.0114

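### The on-treatment laboratory PCST table is labelled treatment-emergent but, as written, does not separate new abnormalities from those already present before brivaracetam

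*SAP*

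**What the plan says.** SAP 11.3.1 plans an on-treatment table of the number and percentage of "subjects with an on-treatment potentially clinically significant treatment-emergent (PCST) value, PCST low value, and PCST high value will be summarized". It takes all results after the first dose and up to the day of the last dose. The denominator is equally broad: "Percentages will be relative to the number of subjects with an on-treatment assessment". Under SAP 3.2.1, "all references to the first dose of BRV in this SAP refer to the first dose of BRV during N01379".

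The limits are in SAP 13.3.1 and 13.3.2 (the latter holds the chemistry criteria, although its heading says hematology). Most are plain cut-offs, such as "≤ 50 mg/dL or ≥ 180 mg/dL" for glucose or "≤ 115 mEq/L or ≥ 155 mEq/L" for adult sodium. One clause refers to baseline, in the ALP/GGT rows for subjects aged 17 or over: "≥ 3 times of ULN, if baseline value ≤ 3 times of ULN".

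On baseline itself, SAP 3.3 says: "Baseline will generally be the last result obtained or prior to the randomization visit of the previous study".

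Protocol 12.3 says that possibly clinically significant treatment-emergent laboratory abnormalities are to be listed, and summarised by period and visit.

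**The concern.** A treatment-emergent count should tell the reader how many subjects developed an abnormality after starting the drug. Neither the counting rule in 11.3.1 nor nearly all of the cut-offs look at what the subject's value was beforehand. A long-standing abnormality is therefore counted like a new one, and repeated laboratory visits over a long follow-up give it many chances to be counted.

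The study has one arm, so no control column shows the background rate of abnormal values. The subject's own pre-treatment value is the natural comparator within the study. At stake is whether the laboratory summary can be read as the label invites. Long-term safety is the primary objective, but laboratory tests are listed among the other safety variables and no hypothesis is tested.

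**Working it through.** **Step 1: which criteria feed the table.** SAP 11.3.1 summarises only parameters planned in the protocol and moves creatinine clearance to listings. Matching the criteria to the panel in Protocol 10.5.1:

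- Hematology: 10 criteria rows, all planned.
- Chemistry: 21 rows, less 6 not planned (BUN, globulin, cholesterol, HDL, LDL, triglycerides), less creatinine clearance: 21 − 6 − 1 = 14.
- Total: 10 + 14 = 24.

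**Step 2: how many have a baseline condition.** There is one clause. It is printed against GGT, but the ALP row lacks an adult line of its own, so it may cover ALP, GGT or both. That leaves 24 − 1 = 23 or 24 − 2 = 22 without one. The row layout may be an effect of text extraction, and the finding does not depend on which reading is right.

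**Step 3: one subject.** Take glucose at or above 180 mg/dL at the prior-study Baseline, at Study Entry and at Month 2. The Month 2 value falls in the window and meets the cut-off, and no rule removes it. The subject counts as on-treatment PCST high.

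**Step 4: the neighbouring criteria.** SAP 13.3.3 requires qualitative urinalysis to rise at least 2 degrees from baseline. SAP 13.3.4 requires a change from baseline for pulse, blood pressure and adult weight. SAP 11.2.1 defines treatment-emergent for adverse events by onset date. Nothing comparable is given for hematology or chemistry.

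**Step 5: can the pre-treatment columns recover the new cases?** SAP 11.3.1 also plans PCST counts at Baseline and Study Entry. Among M subjects with both values, let A meet the cut-off before treatment and B on treatment. New cases then lie between max(0, B − A) and min(B, M − A). With A = 10 and B = 20 (invented, M large), that is 10 to 20. The marginal counts do not settle it.

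**Step 6: size.** The documents give no abnormality rates and state no figure to reproduce. With N subjects, a share pb beyond the cut-off before brivaracetam and a share r of those beyond it again on treatment:

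excess = N × pb × r, at most N × pb.

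N runs from 650 (N01358 lower estimate, none from N01258) to 720 + 100 = 820 (Protocol 5.1.2).

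| pb (assumed) | Upper bound, N = 650 | Upper bound, N = 820 |
|---|---|---|
| 1% | 6.5 | 8.2 |
| 0.1% | 0.65 | 0.82 |

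The share of counted subjects who are not new is pb·r / (pb·r + (1 − pb)·i), where i is the incidence of new cases. With pb from 0.5% to 5%, r from 0.5 to 1 and i from 1% to 3% (all assumed):

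- lowest: 0.0025 / (0.0025 + 0.02985) = 8%
- highest: 0.05 / (0.05 + 0.0095) = 84%

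The width of that range shows that the documents do not fix the size.

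**Step 7: which value is the pre-brivaracetam reference.** In N01358, "subjects will be randomized to an oral dose of BRV 100mg/day, BRV 200mg/day, or to matching PBO" (Protocol 5.4). Baseline precedes that randomisation. For subjects given placebo, the last value before any brivaracetam is Study Entry, taken from N01358 Visit 7 at Week 20 (SAP 3.2.3). This matters for building the fix, not for the present table, which for nearly all parameters consults neither value.

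**The case against.** The strongest reply is that the flag's name already contains treatment-emergent, so a baseline check may be intended and could be set out in a programming specification. A reader might infer from the SAP a decision to count persisting abnormalities as emergent. The documents do not show that; they show an undefined term. But no specification is cited for laboratory PCST, and someone working from the SAP alone has no check to apply. The PCST column at Baseline is not proof either way, because SAP 11.3.2 plans one for urinalysis too, where a shift is required. Attributing the cut-offs to FDA guidelines with sponsor additions explains their origin, not how emergence is judged.

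Mitigation is real. Besides the Baseline and Study Entry PCST counts, the SAP plans change-from-baseline summaries at every later time point including Study Entry, and subject listings. Laboratory findings reported as adverse events follow the onset rule, and Protocol 6.2 excludes subjects whose laboratory values may affect their safety. A reader can see the pre-treatment rate and trace individuals. None of these outputs is a summary of new cases, but together they limit the harm.

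A reader might also infer that using prior-study Baseline miscounts placebo-origin subjects in the current table. It does not, for the reason in step 7, and SAP 3.3 sets that Baseline explicitly for all outcomes.

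Finally, it is tempting to exclude from PCST anyone beyond the limit at the reference. That would hide real worsening: a subject just over an ALT limit beforehand and far above it on treatment would leave the count. The vital-sign rules do not work that way either; they combine a limit with a change. This objection stands and shapes the fix.

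**Conclusion.** The point holds in a limited form: as written, the table cannot be read as a count of new hematology and chemistry abnormalities. It rests on the text of SAP 11.3.1, 13.3.1 and 13.3.2, and on the absence of a laboratory definition elsewhere in the two documents.

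The consequence is minor. Every figure for size in the working depends on assumed prevalence, persistence or incidence, and the effect is likely negligible for extreme limits such as those for adult sodium. The output is descriptive and the error runs towards overstating harm. The documents do not support a claim that safety conclusions would be wrong. The change is worth making because it is cheap and supplies the separation that the label and Protocol 12.3 imply.

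**What to change.** 1. Keep the existing table, but title it as any on-treatment value meeting the PCST cut-off. Label the Baseline and Study Entry columns as values meeting the cut-off.
2. Add a shift table per parameter and direction: PCST status at the pre-brivaracetam reference (not met, met, missing) by worst on-treatment status. Report new cases among subjects who did not meet the cut-off at the reference and have at least one on-treatment value. Subjects already beyond it, including any who worsen, stay visible in their own row.
3. Use the prior-study Baseline as the reference. For subjects randomised to placebo in N01358, also show the shift from Study Entry. Split the table by prior randomised treatment (placebo, BRV), a subgroup that SAP 4.8 now limits to TEAEs.

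The cost is SAP wording, modest programming, a few extra tables and a second reference for one subgroup. Baseline values, Study Entry values and prior treatment are already in the plan. One limit remains: an intermittent abnormality that happened to be absent at the reference will still appear as new.

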2.2 Background information regarding product

Brivaracetam is a chemical relative of the AED levetiracetam (LEV) (Keppra®). Like LEV, BRV displays a high and selective interaction with a novel brain-specific binding site SV2A (synaptic vesicle protein 2A). However, the binding affinity of BRV for SV2A is approximately 10-fold higher. This binding site appears to be the major target for its pharmacological activity. Unlike LEV, BRV also reduces voltage-dependent sodium currents. Brivaracetam also reverses the inhibitory effects of negative allosteric modulators on gamma-aminobutyric acid- and glycine-induced currents. Brivaracetam is extensively metabolized, but seizure protection appears to be associated with the parent compound.

Brivaracetam is rapidly and completely absorbed throughout the gastrointestinal tract. The extent of BRV absorption is not affected by food. The pharmacokinetics (PK) is dose-proportional (at least from 10mg to 600mg). Brivaracetam is weakly bound to plasma proteins ($\leq 20\%$). The volume of distribution is 0.5L/kg, a value that is close to that of total body water. The plasma half-life of BRV is approximately 8 hours in young healthy male adults. The main metabolic pathway of BRV is by hydrolysis of the acetamide group to the corresponding carboxylic acid, while a second pathway is the $\omega 1$ -hydroxylation mediated by cytochrome P450 (CYP)2C19 (with contributions of several other isoenzymes). The combination of these 2 pathways results in the hydroxyacid terminal metabolite. These metabolites are not pharmacologically active. There is no evidence of chiral inversion of BRV. Brivaracetam is eliminated primarily by metabolism and by excretion in the urine. More than 95% of the dose, with less than 9% as unchanged BRV, is excreted in urine within 72 hours after dosing.

Pharmacokinetic studies in elderly subjects and in subjects with renal impairment showed a similar PK profile of BRV compared to that in healthy subjects, while the elimination of the metabolites was markedly slowed down. A PK study in subjects with hepatic impairment showed a 50% increase in exposure to BRV associated with decreased hydroxylation.

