3.2.4 Study periods

The Baseline Period for N01379 corresponds to the Baseline Period of the previous studies, and is defined for seizure outcomes and direct cost parameters. The Baseline Period is defined as study days on or after the date of Visit 1 and prior to the date of Visit 2 for N01258 and study days on or after the date of Visit 1 and prior to the date of Visit 3 for N01358.

The study is divided into 3 periods: Evaluation Period, Down-Titration Period, and Post-Treatment Period. A subject is classified as “discontinued” if the subject has a termination case report form (CRF) or has an early discontinuation visit (EDV). A subject is classified as “completed” if this subject completes the full extent of the study as defined in the protocol at database lock.

A “discontinued” subject can be potentially slotted into the 3 periods of the study. The following algorithms will be used to slot the subject appropriately into the Evaluation Period, Down-Titration Period, and Post-Treatment Period.

- For Evaluation Period, the start date is the date of first dose of BRV, and the following algorithm is used to determine the end date:
 - If the subject enters the Down-Titration Period, then the date of EDV is the end date;
 - If the subject does not enter the Down-Titration Period but meets 1 of the following criteria, the Evaluation Period ends on date of last dose of BRV:
 - Without an EDV but having a termination CRF,
 - With an EDV and having a termination CRF,
 - With an EDV and the date of EDV prior to the database lock date and having no termination CRF.

- A subject is considered entering Down-Titration Period only if the subject has an EDV and at least 1 dose of study drug after the date of EDV, the start date of Down-Titration Period is set as 1 day after the date of EDV, and the Down-Titration Period ends on date of last dose of BRV. A subject without an EDV but having a termination CRF or with an EDV but without any dosing of study drug after the EDV will not have the Down-Titration Period, and no artificial Down-Titration Period will be created for analysis.
- A subject is considered entering the Post-Treatment Period if the subject has at least 1 contact (scheduled visit, unscheduled visit, or telephone contact) after the date of last dose of BRV. The Post-Treatment Period starts 1 day after date of last dose of BRV irrespective of entering the Down-Titration Period, and there is no end date.

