3.2.6 Last Value on BRV Treatment

Last Value for QOLIE-31-P, HADS, and socio-professional data is the last assessment strictly after the date of first dose of BRV and up to and including the YEV at the end of the second year and any EDVs for subjects who did not complete through the YEV at the end of the second year.

Last Value for clinical laboratory parameters, vital signs, and ECGs is the last available result obtained after the first dose of BRV and prior to or on the date of last dose of BRV. All scheduled and unscheduled assessments within this time period will be considered. Last Value will be determined separately for each laboratory parameter for hematology, chemistry, urinalysis, and endocrinology assessments.

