11.2 Adverse events

11.2.1 Definition of treatment-emergent AE

AEs will be classified as either pre-study or treatment-emergent. Pre-study AEs are defined as AEs which had onset prior to the date of the first dose of BRV. TEAEs are defined as AEs that had onset on or after the day of first BRV dose. AEs with an incomplete onset date will be classified as TEAEs if the month and year of onset (when only the month and year are specified) is the same as the month and year of the first BRV dose or the year of onset (when only year is specified) is the same as the year of first BRV dose.

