11.3.4 Microscopic urinalysis

In microscopic urinalysis, a small sample of urine is centrifuged to remove the liquid. The sediment is then examined under a microscope. The number and percentage of subjects with a microscopic urinalysis finding will be summarized. All scheduled and unscheduled assessments after the day of first dose of BRV will be considered. Percentages will be relative to the number of subjects with at least 1 on-treatment microscopic assessment.

Additionally, the number and percentage of subjects with a microscopic finding will be summarized for Baseline, Study Entry, and each visit during the Evaluation Period for which urinalysis parameters were scheduled to be assessed, Last Value, EDV, and FV. Percentages for each parameter and time point will be relative to the number of subjects who had a microscopic assessment at that time point.

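### The cumulative on-treatment laboratory, vital-sign and ECG summaries omit Early Discontinuation Visit results dated after the last dose, and the microscopic urinalysis percentage in SAP 11.3.4 pairs an open-ended numerator with an on-treatment denominator

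*SAP*

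**What the plan says.** SAP 11.3.1 defines two PCST summaries for hematology and chemistry. The cumulative one considers "all assessments after the first dose of BRV and prior to or on the date of the last dose of BRV", with this denominator rule: "Percentages will be relative to the number of subjects with an on-treatment assessment". The by-visit one has rows for Baseline, Study Entry and "each visit during the Evaluation Period for which laboratory parameters were scheduled to be assessed, EDV, Last Value, and FV", and its denominator is the subjects with a value at that time point. The cumulative cut-off recurs for macroscopic urinalysis (11.3.2), endocrinology (11.3.3), vital signs and weight (11.4.1) and the overall ECG table (11.4.2). Last Value in 3.2.6 is "the last available result obtained after the first dose of BRV and prior to or on the date of last dose of BRV". No days are added after the last dose in any of these places.

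SAP 3.2.1 takes the last dose across all study periods, so taper doses count. SAP 3.2.4 foresees subjects who have an EDV but take no dose afterwards. For these subjects "the Evaluation Period ends on date of last dose of BRV".

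SAP 11.3.4 (microscopic urinalysis) uses a different window: "All scheduled and unscheduled assessments after the day of first dose of BRV will be considered". Its denominator is nevertheless the subjects with at least one on-treatment microscopic assessment.

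For adverse events, "TEAEs are defined as AEs that had onset on or after the day of first BRV dose". Protocol 2.2 gives the pharmacokinetic figure: "The plasma half-life of BRV is approximately 8 hours in young healthy male adults".

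**The concern.** Whether an EDV result is counted depends on how the subject stopped. Protocol 5.1.1 plans the EDV first and the taper second, so the EDV of a tapering subject falls before the last dose and is counted. Protocol 5.1.1 and 6.3 accept that some subjects will not taper, and 10.1.6 allows an immediate stop in pregnancy. If such a subject attends a day or more after the last dose, the EDV result is outside the window. Protocol 6.3 names a significant rise in liver enzymes among the reasons for withdrawal, so results near a stop are plausibly informative.

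The omitted result may also be the only recent one. From Month 6, full laboratory panels come every 6 months (Months 6, 12, 18), with liver tests added at Month 9. Last Value for a subject who stops abruptly can therefore be up to about 6 months old.

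In 11.3.4 the percentage itself is at stake, because numerator and denominator do not describe the same period.

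**Working it through.** The SAP states no figure to reproduce: it gives no number or rate of subjects with an EDV after the last dose. The check applies the date rule to cases and then brackets the size under stated assumptions.

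**1. Date rule.** A result counts if first dose < assessment date ≤ last dose date. The stop and EDV days below are invented. Laboratory days 60, 180 and 360 are Months 2, 6 and 12 in 30-day months.

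| Pattern | Last dose | Results on days | Counted | EDV counted? | In denominator? |
|---|---|---|---|---|---|
| A: EDV, then taper | 428 | 60, 180, 360, EDV 400 | all four | yes | yes |
| B: last dose on EDV date | 400 | 60, 180, 360, EDV 400 | all four | yes | yes |
| C: stop, later EDV | 390 | 60, 180, 360, EDV 400 | 60, 180, 360 | no | yes |
| D: stop before Month 2, later EDV | 40 | EDV 47 | none | no | no |

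Pattern D arises because the Month 1 visit has neither laboratory tests nor an ECG (Protocol 8.3), and it assumes no unscheduled test. It does not arise at that point for vital signs, which are taken at Month 1.

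**2. Direction.** In C the denominator is unchanged, so leaving out the EDV can only lower the cumulative count or leave it the same. In D the subject leaves both parts, so the direction depends on that group's abnormality rate. Take 803.6 subjects at 5% (40.18 cases) and add 16.4 pattern-D subjects:
- at a 2% rate: (40.18 + 0.328) / 820 = 4.94%
- at a 10% rate: (40.18 + 1.64) / 820 = 5.10%

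**3. Size, illustrative only.** N is 650 to 820 (Protocol 12.9: 650 to 720, plus up to 100). Assumed, with no source in the documents:
- a share s of 2 to 10% has the EDV after the last dose
- one fifth of these have no on-treatment laboratory result
- the on-treatment PCST rate is 5%
- a share q of 2 to 10% of these EDVs shows a new PCST value

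Percentage with these EDVs counted = [0.05 × N(1 − 0.2s) + q × s × N] / N.
- Low end (N = 650, s = 0.02, q = 0.02): 2.6 subjects outside the denominator, 0.26 abnormalities uncounted, (32.37 + 0.26) / 650 = 5.02%.
- High end (N = 820, s = 0.10, q = 0.10): 16.4 subjects outside the denominator, 8.2 abnormalities uncounted, (40.18 + 8.2) / 820 = 5.90%.

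This counts every late EDV. A 2-day window would recover only part of the shift.

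**4. Residual exposure.** At an 8-hour half-life the fraction left after h hours is 2^(−h/8): 12.5% at 24 h, 3.1% at 40 h (five half-lives), 1.6% at 48 h. A next-day sample still reflects some exposure; one taken weeks later does not.

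**5. SAP 11.3.4.** The On Treatment Period in 3.2.7 ends at the last dose. A subject whose only microscopic assessment after the first dose falls after the last dose can therefore enter the numerator and not the denominator. A subject with a clean on-treatment assessment and a finding at the drug-free FV is counted as a case in a percentage based on on-treatment assessments.

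**The case against.** Ending the on-treatment window at the last dose is what the label literally says, and the SAP pairs it with by-visit rows. That largely stands. Scheduled EDV values are tabulated in the EDV row for every domain, and FV rows exist for all but endocrinology PCST. The ECG listing of clinically significant findings has no upper limit. The EDV row is not a full substitute, because it mixes subjects on and off drug and is not cumulative. Unscheduled laboratory and vital-sign results after the last dose fit no named row, microscopic urinalysis excepted.

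A reader might infer that subjects vanish from the headline safety tables. The documents do not support this. In pattern C only a result is left out, and only pattern D removes a subject. The primary safety variables (SAP 2.2.1.1) are TEAEs, withdrawal due to an AE, and SAEs, and the main TEAE tables extend through the Post-Treatment Period, so an important late finding reported as an AE is captured there. The contrast with TEAEs is not absolute either: the 3-month TEAE tables in 11.2.2 also stop at the last dose.

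A reader might also infer an established net downward bias. That is arithmetic for pattern C but unknown for pattern D. A test that prompts the stop would normally precede the last dose and so be counted; it is the later result that is lost.

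On 11.3.4, one could read on-treatment loosely as any time after the first dose. The two parts would then agree, but the term would conflict with 3.2.7 and the table would differ without explanation from the other laboratory tables.

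**Conclusion.** The point holds in limited form. For subjects who stop without taper and attend the EDV later, that result is missing from the cumulative PCST tables, the overall ECG table and Last Value, whereas a tapering subject's EDV is included. Some very early stoppers have no on-treatment laboratory or ECG result at all. The size cannot be derived from the documents. Under the assumptions above it is at most about 0.9 percentage points on a 5% rate, in a study with no hypothesis testing. Endocrinology is little affected, because Protocol 10.5.1 plans TSH at Yearly Evaluation Visits only.

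The 11.3.4 mismatch needs no assumption: as written, the percentage is wrongly constructed. Overall severity is minor.

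**What to change.** 1. In SAP 11.3.4, apply one window to numerator and denominator, ending where the other on-treatment laboratory tables end.
2. For hematology and chemistry, macroscopic urinalysis, vital signs and weight, and ECG, count scheduled and unscheduled results up to the last dose plus 2 days in the cumulative table. Alternatively, keep the current table and show this one beside it as a supplement. Two days covers five half-lives (5 × 8 = 40 hours) on the protocol's figure, which comes from young healthy men and should be stated as such.
3. Do not label EDV values later than that as on-treatment. Keep the by-visit EDV and FV rows.
4. Reconcile two visit lists that bear on this: SAP 11.4.2 omits the Full Evaluation Visit ECGs in Protocol 10.6.1, and SAP 11.3 and 11.3.3 name endocrinology at the EDV although Protocol 10.5.1 restricts it to yearly visits.

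The cost is a few SAP sentences and a changed date window in programming. The downside is that a few values at low residual exposure enter the cumulative table.
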